- m. Left Ventricular Ejection Fraction required for patients with prior treatment with anthracyclines, or prior treatment with trastuzumab or central thoracic radiation therapy (RT) including exposure of heart to therapeutic doses of ionizing RT, history of myocardial infarction within 6-12 months prior to enrolment or history of other significant impaired cardiac function. For these patients LVEF will be done at screening and thereafter as clinically indicated, and per recommendations following review of initial safety data by the sponsor (see Table 16).
- n. At screening, UPC ≤ 1 , OR proteinuria $\leq 2+$ on two consecutive dipsticks taken no less than 1 week apart, is required. Patients with 2+ proteinuria on dipstick must also have UPC < 0.5 on 2 consecutive samples. Refer to Section 5.2.1.4 for information on management of patients with potential nephrotic syndrome.
- o. Repeat assessment not required on Day 1, if already performed during previous 7 days for screening purposes.
- p. Full Blood Count as per Section 5.2.1.1: hemoglobin, platelets, mean cell volume, white blood cell count, absolute neutrophil count and absolute Lymphocyte count
- q. Biochemistry (sodium, magnesium, calcium, potassium, albumin, total protein, creatinine, total bilirubin, AL.T, AST, alkaline phosphatase). Creatinine clearance (Cockcroft-Gault or another validated method); to be calculated at baseline and re-calculated as clinically indicated during study conduct.
- r. Baseline tumor assessment should include CT/MRI of the chest, abdomen and pelvis. Follow-up CT/ MRI tumor assessments will cover chest (in those patients with disease in the chest or upper abdomen lymphadenopathy at baseline), abdomen and pelvis. Any other sites at which new disease is suspected should also be appropriately imaged. Baseline radiological imaging is required within 4 weeks prior to first dose of investigational products (IPs). Follow up assessments should be done every 8 weeks after first dose of IP until objective radiological disease progression, withdrawal of consent or the primary analysis.
- s. Blood samples for PBMC testing (8 mL) and plasma biomarker testing (6 mL) will be taken at baseline; at Week 4; at Week 8 and treatment discontinuation. Details to be found in the lab manual.

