5.2.1.2 Biochemistry assessments for safety

- Sodium
- Potassium
- Calcium
- Magnesium
- Creatinine
- Total bilirubin
- Alkaline phosphatase [ALP]
- Aspartate transaminase [AST]
- Alanine transaminase [ALT]
- Total protein
- Albumin

In addition, samples for the measurement of thyroid stimulating hormone (TSH) and free thyroxine (FT4) are to be collected at screening, every 8 weeks during the treatment period, and for patients continuing to receive clinical benefit without meeting any discontinuation criteria during the study, at the FPV. The Investigator should make an assessment of the available results with regard to clinically relevant abnormalities. The laboratory results should be signed and dated and retained at center as source data for laboratory variables. For information on how AEs based on laboratory tests should be recorded and reported, see Section 6.3.

NB. In case a patient shows an AST or ALT $\geq 3 \times \text{ULN}$ and total bilirubin $\geq 2 \times \text{ULN}$ please refer to Appendix D ‘Actions required in cases of combined increase of Aminotransferase and Total Bilirubin – Hy’s Law’, for further instructions.

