6.3.7 Adverse events based on examinations and tests

The results from protocol mandated laboratory tests and vital signs will be summarized in the CSR. Deterioration as compared with baseline in protocol-mandated laboratory values, vital signs and ECG abnormalities should only be reported as AEs or SAEs if one of the following is met:

- Any criterion for an AE or SAE is fulfilled
- Causes discontinuation of IPs
- Causes IP interruption
- Causes IP dose reduction
- The abnormality is considered clinically significant by the Investigator

If deterioration in a laboratory value/vital sign is associated with clinical signs and symptoms, the sign or symptom will be reported as an AE and the associated laboratory result/vital sign will be considered as additional information. Wherever possible the reporting Investigator uses the clinical, rather than the laboratory term (eg, anemia versus low Hb value). In the

absence of clinical signs or symptoms, clinically relevant deteriorations in non-mandated parameters (ie, those not described in [Table 5](#)) should be reported as AE(s).

Deterioration of a baseline laboratory value or condition, which is unequivocally due to disease progression, should not be reported as an AE/SAE.

Any new or aggravated clinically relevant abnormal medical finding at a physical examination as compared with the baseline assessment will be reported as an AE.

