6.8.3.5 Management of Thyroid Toxicities

The use of cediranib has been associated with elevations of TSH and patients should be managed as per Table 15. In all cases, IPs should continue unless clinically contraindicated. Referral to an endocrinologist should also be considered if thyroid abnormalities occur.

Table 15 **Monitoring and Management of Thyroid Toxicities**

Result of TSH and FT4	Action
Increases of TSH with normal FT4	Monitor
Increases in TSH with normal FT4 and adverse events suggestive of incipient hypothyroidism	Consider replacement thyroxine
Increase in TSH with reductions in FT4	Consider replacement thyroxine

Abbreviations: FT4 free thyroxine; TSH thyroid stimulating hormone

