3.3.4 Clinical chemistry, haematology and urinalysis

Blood and urine samples for determination of clinical chemistry, hematology, and urinalysis will be taken at the following times:

- Hematology and Biochemistry data will be taken during screening, at day 1, weekly till week 4, every 2 weeks till week 8, and every 4 weeks from week 8 onwards. If the study treatment is discontinued then a blood sample will be taken at this time and during the day 30 follow-up visit
- A urine dipstick will be conducted during screening, at day 1, and every 4 weeks from week 8 onwards. If the study treatment is discontinued then a blood sample will be taken at this time and during the day 30 follow-up visit

Additional safety samples may be collected if clinically indicated at the discretion of the Investigator. The date, time of collection and results (values, units and reference ranges) will be recorded on the appropriate eCRF.

The clinical chemistry, hematology and urinalysis will be performed at a local laboratory at or near to the Investigator site. Sample tubes and sample sizes may vary depending on laboratory method used and routine practice at the site.

The following laboratory variables will be measured:

Table 7 Laboratory safety variables

Clinical chemistry (Serum/Plasma)	Haematology (Blood)	Urinalysis (Urine)
Albumin	Hemoglobin	Protein
Alanine Transaminase (ALT)	Platelet counts	
Aspartate Transaminase (AST)	Mean Cell Volume (MCV)	
Alkaline Phosphatase (ALP)	White Blood Cell count (WBC)	
Bilirubin, total	Absolute Neutrophil Count (ANC)	
Calcium	Absolute Lymphocyte Count	
Creatinine		
Magnesium		
Potassium		
Sodium		

All values will be classified as low (below range), normal (within range) and high (above range) based on project-specific reference ranges ([Appendix A](#)). Patient with urine protein ≥ 3.5 g/24 hours (CTCAE Grade 3 according to CTCAE v4) or urinary protein/creatinine ratio of >3.5 should be considered as nephrotic-range proteinuria.

Changes from baseline to each visit for all patients who have a baseline laboratory test and the corresponding post-baseline laboratory test will be calculated as the post-baseline test value minus the baseline test value, where baseline is the latest non-missing value collected prior to the first dose of study drug

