- At least one AESI causally related to either study medication separately
- At least one AESI leading to discontinuation of either study medication separately

A summary of total duration (days) of AESI will be provided for events which have an end date and this will be supported by summaries of ongoing AESIs at death and, separately, at data cut-off.

To reflect the particular interest in diarrhoea, fatigue, hypertension, and nausea, life tables and prevalence plots will be produced for these AEs.

In addition as all CTCAE grade changes for diarrhoea, fatigue, hypertension, and nausea will be recorded, a plot will be generated for each AE which shows the AE grade over time for each patient.

Laboratory evaluations

All laboratory data recorded in the eCRF will be listed. If any additional analyses to those in [Table 7](#) are also recorded then these will be listed only. Out-of-reference range values will be flagged as high (H) or low (L) in the listings.

For clinical chemistry and haematology, numerical summaries will be generated which include the mean, standard deviation, median, minimum value, maximum value, and lower and upper quartiles at each visit in which laboratory values are taken. Plots of both the maximum post-baseline ALT and AST versus the maximum post-baseline total bilirubin, expressed as multiples of their upper limit of reference range will be produced.

As a primary interpretation of potential drug induced liver injury, outputs related to patients with liver function tests (LFTs) that meet biochemical criteria for Hy's Law and with elevations of LFTs will be produced. Biochemical criteria for Hy's Law are defined as any situation where a study patient has an increase in both AST or ALT $\geq 3 \times \text{ULN}$ and TBL $\geq 2 \times \text{ULN}$, irrespective of ALP, at any point during the study. The elevations do not have to occur at the same time or within a specified time frame.

For all patients who meet the criteria for potential Hy's Law, a plot of AST, ALT, ALP and total bilirubin over time will be produced.

The proportion of patients who met GCIG criteria for CA-125 progression (any of the criteria, and each criterion individually) will be summarised by visit. The time to CA-125 progression will be presented using a Kaplan Meier plot and the median time to CA-125 progression (from the Kaplan Meier) calculated. Patients without CA-125 progression will be censored at their latest lab evaluation visit.

Vital signs

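### SAP Table 7 omits TSH, FT4 and total protein, so these protocol-mandated tests are only listed, and no planned output gives a rate or change from baseline for thyroid function

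*SAP*

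**What the plan says.** **Protocol.** Section 5.2.1.2 lists the routine biochemistry, including total protein, and adds that "samples for the measurement of thyroid stimulating hormone (TSH) and free thyroxine (FT4) are to be collected at screening, every 8 weeks" during treatment, and at the Final Protocol Visit for continuing patients. Table 5 has a separate row for TSH and FT4, and its footnote q repeats the chemistry list: "Biochemistry (sodium, magnesium, calcium, potassium, albumin, total protein, creatinine, total bilirubin", followed by the liver enzymes. Section 6.3.7 commits to reporting: "The results from protocol mandated laboratory tests and vital signs will be summarized in the CSR". Section 6.8.3.5 says "The use of cediranib has been associated with elevations of TSH" and sets out monitoring in Table 15 by TSH and FT4 result. The safety objective (Section 2.3) takes treatment-emergent changes in laboratory parameters as an outcome measure.

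**SAP.** Section 3.3.4 introduces Table 7 with "The following laboratory variables will be measured". The table has ten chemistry variables and does not include TSH, FT4 or total protein. Section 4.2.9 promises: "For clinical chemistry and haematology, numerical summaries will be generated which include the mean, standard deviation, median" and other statistics at each visit. For tests outside Table 7, the same section says that if they "are also recorded then these will be listed only". Section 6, on changes from the protocol, declares one item only: the 10-point threshold for symptom improvement.

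**The concern.** A rule in the SAP gives three mandated tests less than the protocol promises. For total protein this is a matter of consistency. For TSH and FT4 it leaves a toxicity that the protocol names, monitors on a fixed schedule and manages by laboratory result without any planned laboratory summary.

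The protocol gives several reasons to expect a thyroid signal. Section 1.1.2.2 reports hypothyroidism as more common during cediranib maintenance in the earlier randomised trial. Inclusion criterion 13 requires adequately controlled thyroid function at entry. Section 6.8.3.3 names thyroid function among the possible causes of fatigue, and fatigue receives life tables, prevalence plots and grade-over-time plots in the SAP. A reader of those fatigue outputs would have no thyroid summary to set beside them.

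**Working it through.** No sample size, power or event figure is involved, and the plan states no figure to reproduce. The check compares the test lists, then applies the SAP's rule.

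**1. Compare the lists.**

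| Group | Protocol (5.2.1.1, 5.2.1.2, Table 5) | SAP Table 7 | Difference |
|---|---|---|---|
| Routine chemistry | 11 | 10 | 1 (total protein) |
| Thyroid | 2 (TSH, FT4) | 0 | 2 |
| Chemistry and thyroid together | 11 + 2 = 13 | 10 | 13 − 10 = 3 |
| Haematology | 6 | 6 (the same six) | 0 |

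Every chemistry test in Table 7 is in the protocol list, so the difference is exactly these three tests.

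**2. Apply the listing rule.** All three are outside Table 7, so under SAP 4.2.9 they appear in listings only. CA-125 is also outside Table 7, but it has its own derivation (SAP 3.3.4.1) and its own outputs (a progression summary by visit and a Kaplan-Meier plot in 4.2.9). TSH and FT4 have neither. The sampling text in SAP 3.3.4 does not mention thyroid tests.

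**3. Set the two commitments side by side.** Protocol 6.3.7 promises a summary of mandated laboratory results and makes no exception. Protocol 8.5.2 leaves safety detail to the SAP, but still describes the presentation as summaries and descriptive statistics, as does the opening of SAP 4.2.9. A patient-level listing is neither.

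**4. Look for another output that would carry the information.**
- Adverse events of special interest: thyroid events are in neither the protocol list (6.1.1) nor the longer SAP lists (3.3.3, 4.2.9). No grouped table captures them.
- Ordinary adverse event tables: reported hypothyroidism would appear by system organ class and preferred term, by maximum grade and by causality.
- Whether a laboratory change becomes an adverse event: under protocol 6.3.7, deterioration in a mandated test is reported if it meets an adverse event criterion, leads to discontinuation, interruption or dose reduction, or is judged clinically significant. Protocol 6.8.3.5 says that treatment continues through thyroid abnormalities unless clinically contraindicated, and Table 15 calls only for monitoring when TSH rises with normal FT4 and no suggestive events. The triggers tied to a change in dosing will therefore seldom apply. An asymptomatic rise reaches the adverse event tables mainly if the investigator judges it clinically significant.
- Listings: SAP 4.2.9 flags out-of-range values as high or low.

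**5. Result.** Thyroid results at screening and every 8 weeks, for about 60 planned patients, are collected and listed. No planned output gives the proportion with raised TSH or low FT4, or the change from baseline in either.

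**The case against.** The strongest case against is that little is lost. All laboratory data on the eCRF are listed with high and low flags, and with about 60 patients the abnormal values can be counted by hand. Clinically significant thyroid abnormalities still reach the adverse event tables. The reporting sentence in 6.3.7 stands in the section on recording adverse events, not in protocol Section 8, and Section 8 gives no laboratory list and refers safety detail to the SAP. It is therefore arguable whether SAP Section 6 had to declare anything. Thyroid events are not of special interest in either document. The trial has one arm, so a TSH table would be descriptive only.

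Much of this stands, and it rules out some stronger readings that a reader might infer:
- *The CSR could not say how many patients had raised TSH.* The flagged listings would allow a count; what is missing is a planned summary.
- *The adverse event tables would miss thyroid toxicity.* They need not show asymptomatic rises that were not judged significant, but they would show reported hypothyroidism.
- *Section 6.3.7 covers every laboratory test in so many words.* It does not say so; it refers to mandated tests and makes no exception.
- *Total protein carries a safety risk of its own.* Neither document ties a toxicity or a decision to it.

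The objection does not remove the conflict. Delegating detail to the SAP does not turn a promised summary into a listing, and a safety objective that includes treatment-emergent laboratory changes is poorly served by hand counts.

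**Conclusion.** The point holds as a conflict between the documents with a limited but real consequence. Three of 13 mandated chemistry and thyroid tests are reduced to listings, contrary to protocol 6.3.7 and without a declaration in SAP Section 6. For TSH and FT4, a named cediranib toxicity has no planned rate or change-from-baseline summary. No data are lost, and no efficacy result or decision rule is affected. It should be corrected before database lock, but it does not threaten the trial's main conclusion.

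Two assumptions apply. SAP Appendix A, whose contents were not available to me, is taken to hold reference ranges only; the listing rule is tied to Table 7, so ranges would not alter it. The omission is taken to be an oversight, because Table 7 is presented as the set of laboratory variables to be measured; if it was deliberate, it needs to be declared.

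**What to change.** 1. Add TSH and FT4 to SAP Table 7, so that they receive the by-visit and change-from-baseline summaries given to other chemistry tests. Add total protein as well, solely to agree with the protocol.
2. Add one descriptive table of patients with any post-baseline TSH above range, split by FT4 status (normal or below range), with baseline TSH and FT4 status shown. These categories are a reporting device and are not the wording of protocol Table 15, which speaks of increases and reductions and has a further row for suggestive adverse events. By-visit summaries alone would not be enough: SAP 4.1.3 drops visits with too few observations, and with 60 patients both of its limits equal 20 (60 / 3 = 20).
3. State which reference ranges define above and below range. SAP 3.3.4 classifies values by project-specific ranges in Appendix A, while testing is done at local laboratories and local ranges are recorded on the eCRF.
4. If the sponsor prefers to keep these tests in listings, record that in SAP Section 6 as a departure from protocol 6.3.7, with the reason.

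The cost is two or three extra descriptive tables from data already collected. No visit, sample or efficacy analysis changes.

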Appendix D Actions Required in Cases of Increases in Liver Biochemistry and Evaluation of Hy's Law

INTRODUCTION

This Appendix describes the process to be followed in order to identify and appropriately report cases of Hy's Law. It is not intended to be a comprehensive guide to the management of elevated liver biochemistries.

During the course of the study the Investigator will remain vigilant for increases in liver biochemistry. The investigator is responsible for determining whether a patient meets potential Hy's Law (PHL) criteria at any point during the study.

The Investigator participates, together with AstraZeneca clinical project representatives, in review and assessment of cases meeting PHL criteria to agree whether Hy's Law (HL) criteria are met. HL criteria are met if there is no alternative explanation for the elevations in liver biochemistry other than Drug Induced Liver Injury (DILI) caused by the Investigational Medicinal Product (IMP).

The Investigator is responsible for recording data pertaining to PHL/HL cases and for reporting Adverse Events (AE) and Serious Adverse Events (SAE) according to the outcome of the review and assessment in line with standard safety reporting processes.

DEFINITIONS

Potential Hy's Law (PHL)

Aspartate Aminotransferase (AST) or Alanine Aminotransferase (ALT) $\geq 3x$ Upper Limit of Normal (ULN) **together with** Total Bilirubin (TBL) $\geq 2xULN$ at any point during the study following the start of study medication irrespective of an increase in Alkaline Phosphatase (ALP).

Hy's Law (HL)

AST or ALT $\geq 3x$ ULN **together with** TBL $\geq 2xULN$, where no other reason, other than the IMP, can be found to explain the combination of increases, eg, elevated ALP indicating cholestasis, viral hepatitis, another drug.

For PHL and HL the elevation in transaminases must precede or be coincident with (ie, on the same day) the elevation in TBL, but there is no specified timeframe within which the elevations in transaminases and TBL must occur.

IDENTIFICATION OF POTENTIAL HY'S LAW CASES

In order to identify cases of PHL it is important to perform a comprehensive review of laboratory data for any patient who meets any of the following identification criteria in isolation or in combination:

- ALT \geq 3xULN
- AST \geq 3xULN
- TBL \geq 2xULN

The Investigator will remain vigilant for local laboratory reports where the identification criteria are met, where this is the case the Investigator will:

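### SAP 4.2.9 labels patients as potential Hy's Law without the order and post-first-dose conditions of Protocol Appendix D, so its set can be larger than the protocol's

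*SAP*

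**What the plan says.** SAP 4.2.9, under laboratory evaluations, plans outputs for patients who meet the biochemical criteria for Hy's Law: AST or ALT of at least 3×ULN and TBL of at least 2×ULN, "irrespective of ALP, at any point during the study". On timing it adds only this: "The elevations do not have to occur at the same time or within a specified time frame". The next paragraph plans a plot of liver tests over time, introduced with "For all patients who meet the criteria for potential Hy's Law". It therefore gives the same patients the name that the protocol defines.

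Protocol Appendix D defines PHL with the same thresholds, but "at any point during the study following the start of study medication irrespective of an increase in Alkaline Phosphatase". It then adds an order condition: "For PHL and HL the elevation in transaminases must precede or be coincident with (ie, on the same day) the elevation in TBL". The same sentence continues "but there is no specified timeframe within which the elevations in transaminases and TBL must occur". Hy's Law (HL) proper is PHL with no explanation other than the study drug, as agreed after review.

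SAP Section 6, which lists changes from the protocol, contains one entry, on the quality-of-life improvement threshold. It does not mention Hy's Law.

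**The concern.** One label carries two definitions. The SAP presents this output as its main reading of possible drug-induced liver injury, so a CSR reader will take a patient shown there as meeting the protocol's PHL criteria. Under the SAP rule, a patient whose bilirubin rose and resolved before her transaminases rose is included. Under Appendix D she is not.

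What is at stake is traceability. In Appendix D, the discussion with the study physician, the work-up of cause, the three Liver CRF modules and the joint causality review all follow from PHL being met. A patient whom the site has properly recorded as not meeting PHL has none of these. If the CSR then shows her as potential Hy's Law, no assessment stands behind the label and nothing explains the difference. Liver failure is an adverse event of special interest for cediranib (Protocol 6.1.1), so an unexplained entry would draw questions.

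**Working it through.** The plan states no figure for this item, so there is none to reproduce. The check is a comparison of the two rules.

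**Step 1. Conditions side by side**

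| Condition | SAP 4.2.9 | Protocol Appendix D (PHL) |
|---|---|---|
| AST or ALT | ≥3×ULN | ≥3×ULN |
| TBL | ≥2×ULN | ≥2×ULN |
| ALP | disregarded | disregarded |
| Time window between elevations | none | none |
| Order | not mentioned | transaminase before, or same day as, TBL |
| Period | any time in the study | after start of study medication |

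The documents differ in the last two rows only. The SAP sentence about timing is compatible with Appendix D. The conflict lies in the absent order condition and in the period given in the sentence before it.

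**Step 2. The rules as logic**

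Let *a* be any day with an elevated transaminase and *b* any day with an elevated TBL, with first dose on Day 1.

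- SAP: some *a* exists and some *b* exists.
- Protocol: some *a* ≥ 1 and some *b* ≥ 1 exist with *a* ≤ *b*.

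The protocol rule implies the SAP rule. The SAP count is therefore always equal to or greater than the protocol PHL count.

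**Step 3. Eight illustrative timing patterns**

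| Transaminase elevated on day | TBL elevated on day | SAP | Protocol |
|---|---|---|---|
| 15 | 29 | yes | yes |
| 15 | 15 | yes | yes |
| 15 | 197 | yes | yes |
| 29 | 15 and still on 29 | yes | yes* |
| −7 and 8 | 15 | yes | yes |
| 29 | 15 only | yes | no |
| −7 only | 15 | yes | no |
| −7 only | −7 only | yes | no |

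*Yes if order is judged on any elevated value; no if judged by first onset. Appendix D does not say which.

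Three patterns separate the rules: one through order and two through the pre-dose period. These are constructed cases that show where the rules part. They say nothing about frequency.

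**Step 4. Reach of the pre-dose part**

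Inclusion criterion 11 (Protocol 3.1) limits bilirubin to 1.5×ULN and AST/ALT to 3×ULN within 28 days before dosing. A pre-dose TBL of 2×ULN or more is thus unlikely in an eligible patient. A pre-dose transaminase value that counts would have to sit exactly at the limit of 3×ULN, or come from another sample.

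**Step 5. What happens to a bilirubin-first patient**

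Under Appendix D, any one of ALT ≥3×ULN, AST ≥3×ULN or TBL ≥2×ULN starts a review. The investigator notifies the sponsor's representative, repeats the test, completes the unscheduled laboratory CRF modules and checks reports from earlier visits. If PHL is judged not met, the sponsor is told so and follow-up is routine. The formal PHL assessment and the three Liver CRF modules are not started.

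**Step 6. Size**

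With the planned 60 patients, one affected patient is 1/60 = 0.0167, or about 1.7 percentage points.

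**The case against.** The strongest case is that the SAP set is a deliberately broad biochemical screen. It misses no protocol case. The plots over time and the full laboratory listings let a reader see the order of the elevations and the ALP. No endpoint or decision rule depends on it. All of this stands, and it is why the point is minor. It does not remove the point, because the SAP uses the protocol's term for the broader group and declares no change.

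Three stronger readings are tempting, and the documents do not support them.

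- A reader might infer that the CSR output will fail to match the reported cases. The sets can differ; they need not. Reported HL cases also depend on a causality judgement, so the fair comparison is SAP biochemical cases against protocol PHL cases.
- A reader might infer that sites would never raise a bilirubin-first patient. Step 5 shows that notification, repeat testing and a look back at earlier results would still take place.
- A reader might infer that the order rule is what screens out biliary obstruction by tumour. If TBL is still at least 2×ULN when the transaminase reaches 3×ULN, the two coincide on that day and the rules may agree. Appendix D itself handles cholestasis at the causality step.

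On the pre-dose part, Protocol 4.2 starts the study conduct period at the first dose, so the SAP's period could be read as post-dose. Appendix D, however, adds the start of medication as a separate limit and also speaks of PHL criteria met at visits before treatment. The wording is worth settling, but little turns on it.

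**Conclusion.** The difference is real and undeclared. SAP 4.2.9 omits Appendix D's order condition and its post-first-dose limit while keeping the protocol's name for the patients. The SAP set can only equal or exceed the protocol PHL set. The clear case of excess is bilirubin that has fallen before the transaminase rises. The pre-dose route is possible but unlikely given eligibility.

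No frequency can be derived from the documents. The figure of 1.7 percentage points per patient assumes a denominator of 60, and any assumed number of such patients would be a guess. A reader might infer a missed safety signal; the containment shown in step 2 rules that out. This is a minor correction of labelling and traceability.

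**What to change.** In SAP 4.2.9, restrict the Hy's Law derivation to post-first-dose values and choose one of two routes:

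1. Apply the Appendix D order condition, and list patients who meet the thresholds in the other order separately under their own label.
2. Keep the broader set, call it a biochemical screen, and flag the Appendix D PHL subset within it. The term potential Hy's Law is then used for that subset only.

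Under either route, state whether order is judged by first onset or by any elevated value, since this decides the case where bilirubin stays elevated. Record any remaining difference from Appendix D in SAP Section 6.

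The cost is a few sentences in the SAP and a date comparison in the program. No new data are needed.
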